Soy isoflavone pills and maltodextrin placebo pills. The make-up of the isoflavones is the same as that which exists naturally in soy. We believe studying the effect of the two soy isoflavones at their naturally occurring ratio is a pre-requisite to contemplating a study that addresses the effect of different ratio or the individual isoflavone. The total amount of isoflavones in each tablet will be maintained constant through formulation. The formulation consists of, for example, 125 mg Novasoy (50 mg of total isoflavones as aglycones) or equivalent weight of placebo material, 60 mg sorbitol, 3 mg magnesium stearate, 412 mg dicalcium phosphate with a total of 600 mg per tablet. [Note: Volunteers in this study will take 2 pills (=120 mg isoflavones as aglycones) per day.] For placebo, 10-DE maltodextrin (90% weight) and RT-175 caramel color (10% by weight) will be substituted for Novasoy [Note: Volunteers will take 2 tablets per day.] The relative amount of genistein/genistin to daidzein/daidzin does vary between lots of soybeans and this variation is a natural phenomenon. This ratio for Novasoy has varied between 1.1 to 1.3 (mean \pm SD: 1.2 ± 0.1) from lot-to-lot. However, we will use only one lot of Novasoy for the entire study. Therefore, the relative amount of the two isoflavones will be constant. All subjects (both treatment and placebo) will be given required daily intake of multi-vitamin and minerals. Vitamin pill will be packaged with treatment assignment pill in container for daily dosage and consumption.

Breast density: Breast density of subjects will be determined by both mammography and bilateral breast MRI at the outpatient Radiology Clinic at UTMB. Both tests will be performed during the luteal phase, as confirmed by obtaining a blood sample on the days of the breast density tests for measuring progesterone.

MRI is superior to mammography for measuring parenchymal pattern (dense tissue) of the breasts, because density measurement by MRI is more objective, and thus more accurate, than the subjective scoring in mammography. Moreover, MRI does not require breast compression and does not involve radiation exposure, which will make it easier to study density changes in younger women in the future. Hence from the scientific point of view, MRI as an outcome measure is preferable. However, for practical translation of our study results to large populations, mammography as an end point for measuring density changes in population-based interventions is more feasible than MRI. The cost of mammography is approximately one-eighth that of MRI, and is customarily covered by insurance. Furthermore, most clinics are better equipped to perform mammography than breast MRI. Hence the efficacy of our pill supplementation interventions will be measured by two outcome measures, one of which will maximize scientific value, and the other to allow our results to be more readily compared to other reports and be more readily translated to standard clinical care.

Mammography: This test will be performed with a digital mammographic unit, a Senograph 2000D, S30311AR, a new Full Field Digital Mammography System (GE Medical Systems, Milwaukee, Wisconsin 53201). A routine quality control program includes sensitometric evaluation, phantom imaging, and regular visit by a medical physicist ([name]). The instrument setting and breast compression will be duplicated and maintained for each woman for baseline and intervention mammography. The operator for the mammography will have the pre-diet imaging parameters for each woman on hand as a reference for all mammography. Screening mammograms include 4 views, 1 craniocaudal and 1 mediolateral views for each breast. Duplicate craniocaudal view will be performed for left breast, i.e. a total of 5 views for the study per subject.

One craniocaudal and one mediolateral digitized mammographic images will be randomly selected from each breast. Within each subject, the baseline and intervention period films will be matched for view as well as for breast. Quantification will be performed by subjective visual scoring using BI-RADS as well as by objective computer-assisted automatic measurement patterned after that described by Boyd et al. with modification. Digitized mammographic images from each subject before and after pill intervention will be coded in random order, networked to a personal computer for image processing and interpretation by a radiologist for independent scoring using BI-RADS. Radiologist will have no knowledge of pill assignment or dates of mammography and will determine the density using BI-RADS™ and rank the relative densities of images from baseline and intervention (categorical variable). The BI-RADS categories are: 1) entirely fatty (<25% dense area), 2) fatty with scattered fibroglandular tissue (25-50% dense area), 3) heterogeneously dense (50-75% dense area), and 4) extremely dense (>75% dense area).

The digitized images of these mammograms will be used for measuring areas of dense and non-dense tissues using a free image analysis software ImageTool. This software uses a histogram segmentation to assess dense tissue. Briefly, the reader selects a grayscale threshold value differentiating the entire breast tissue and a second threshold delineating only the dense tissue. Binary masks are made from each threshold value (the

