Research Protocol (revised July 7, 2014)

Project Title: Mammographic Density and Soy Isoflavones

Principal Investigator: [name].

Dept of Preventive Medicine and Community Health
University of Texas Medical Branch, [name]
[contact]
[contact]
[contact]

Abstract. Populations consuming high levels of soy, as in many Asian countries, have lower levels of ovarian hormones, lower rates of breast cancer, and reduced mammographic density than populations consuming typical Western diets. These observations may in part be explained by our clinical studies that found ovarian hormone levels of premenopausal women to be lowest while they were consuming a diet that provided 15% energy from soymilk containing weakly estrogenic isoflavones. No adverse effects were observed. Further questions are whether isoflavones are the critical components influencing breast cancer risk and whether they do so by affecting other reversible risk markers for breast cancer, such as breast density. Women with dense breasts have a 4-6 fold excess risk of developing breast cancer. Moreover, greater breast density makes it more difficult to detect early breast cancer by mammography. To test the hypothesis that consumption of soy isoflavones reduces breast density, we propose a randomized, double-blind study, with two arms, and 100 premenopausal women in each arm. Women will be recruited and randomly allocated to take soy isoflavone pills (treatment) or placebo pills containing no isoflavones (control) for 2 years. The daily dose will be 120 mg of total isoflavones. Both treatment and placebo pills will contain multi-vitamin and minerals. Women will provide blood and urine samples before and during the supplement intervention period for the analyses of ovarian hormones and isoflavones. At baseline and after the intervention period, subjects will be examined for breast density by mammography and magnetic resonance imaging. The efficacy of the intervention will be determined by comparing mean changes of dense breast tissue over the 2-year intervention period in the two groups with adjustment for baseline values and individual patient characteristics of interest. We hypothesize that 1 to 2 years of a soy isoflavone supplement in premenopausal women will reduce the effects of endogenous estrogens and reduce progesterone levels further, which will explain a corresponding decrease in breast density. Our research results will have significant implications for breast cancer risk reduction. Reducing breast density can be expected to reduce the volume of target tissue at risk for breast cancer development and will improve the sensitivity of mammography for screening. The study may lead to a novel, non-invasive and economical approach to breast cancer prevention.

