Experimental Design and Methods: These aims will be achieved by a prospective, parallel 2-arm, repeated measures, randomized, double blind, placebo controlled study. After a successful completion of a 2-month baseline observation, qualified women will be randomly allocated to either placebo pills (control) or 120 mg isoflavone pills (aglycones, treatment) 5 days per week for 2 years with blinding of subjects, research staff and investigators to the supplement assignments. Both treatment and placebo pills will contain required daily intake of multi-vitamin and minerals. The main outcomes are: 1) breast density by mammography and MRI, 2) bone density by dual energy x-ray absorptiometry (DEXA) and 3) serum, nipple aspirate, and urinary levels of estrogens, progesterone, and other breast cancer risk markers, and changes from baseline to intervention. The explanatory variables are nutrient intakes, isoflavone intakes, urinary and plasma levels of isoflavones, demographic data (body weight, height), and reproductive history. Breast (and bone) density is chosen as a major outcome of interest because it is an index of cumulative exposure to ovarian hormones and is postulated to be intermediate biomarkers for breast cancer risk (6). To monitor safety, blood chemistries including liver and thyroid function tests, lipid profiles, blood cell counts, menstrual cycle lengths, and cytology of nipple fluid aspirates (to determine presence or absence of hyperplastic epithelial cells), endometrial histology, vaginal smear cytology, unexpected vaginal bleeding, breast lumps, and bone density will be monitored once every three months during all outpatient visits.

Inclusion/exclusion criteria: Women must be 30-40 years of age with regular cycles, FSH levels \leq 10 mU/ml and mid-luteal phase progesterone $>$ 8 ng/ml. Mammograms must be normal. Exclusions include use of contraceptive agents, other exogenous hormones, medications known to affect mammographic density, any medically prescribed diet, current pregnancy or lactation, previous history of cancer, breast cancer in a first degree relative, breast augmentation, reduction, or lifting, and per- or postmenopausal status.

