 13. After completing 12 months of pill supplement, subjects will complete another Harvard DAQ (recall food intake frequency for the past 12 months of pill intervention) and will be given a pregnancy test, followed by a mammography, a breast MRI, and a DEXA bone density test.

14. Subjects will continue consumption of the assigned pill, have the 1-day visit to GCRC for blood draw and other study procedures once every three months (e.g. repeat steps 6 to 14) for another 12 months.
15. Pregnancy test will be performed whenever cycle length increases by >30% of each subject's usual length. Pregnancy test will also be performed no longer than 48 hrs prior to taking mammography and DEXA tests to ensure that pregnant women are not exposed to radiation. Gynecological examination including Pap smear will be done at the end of the study.
16. Transvaginal probe ultrasonography and endometrial biopsies will be performed when medically indicated, for example, if amenorrhea develops. This will be performed by Dr. [name].

Risk and Benefit Assessment:

The soy isoflavone are currently available as pills over-the-counter and are found in soy foods sold to the public. We will use isoflavone tablets provided by the Archer Daniel Midland Co., which we have used in the past several years for several preliminary studies. These isoflavones are isolated by repeated alcohol extractions of soy protein isolates or soy protein concentrates (different processing). Alcohol is then removed by evaporation and the residues used for tablet formulation. In this way, the make-up of the isoflavones is the same as that which exists naturally in soy. These pills are sold as nutritional products over-the-counter to the public. The placebo pills contain maltodextrin, a carbohydrate, and should have no biological effect at the dose, 150 mg, to be given to the subjects.

Populations consuming soy have reduced risk of breast and endometrial cancers, reduced mammographic density, and reduced hip fracture rate. The FDA has approved a health claim regarding soy consumption and risk reduction for cardiovascular diseases. There are no other known risks from soy isoflavones from population-based studies, as soy products are commonly consumed in many countries. However, adverse effects have not been previously looked for carefully, so it is possible that there are unknown risks.

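### Two of the only tablets described supply 100 mg of isoflavones, not the stated 120 mg, and the 150 mg placebo figure has no stated basis and does not match that tablet

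*Combined protocol and SAP*

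**What the plan says.** Three places give the same dose.

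- The Abstract: "The daily dose will be 120 mg of total isoflavones".
- Experimental Design and Methods: "120 mg isoflavone pills (aglycones, treatment) 5 days per week for 2 years".
- The Methods paragraph on the soy isoflavone and placebo pills: "Volunteers in this study will take 2 pills (=120 mg isoflavones as aglycones) per day".

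That Methods paragraph also holds the only tablet formula in the document, and it introduces the formula as an example. The active ingredient is "125 mg Novasoy (50 mg of total isoflavones as aglycones"). The rest is 60 mg sorbitol, 3 mg magnesium stearate and "412 mg dicalcium phosphate with a total of 600 mg per tablet". For the placebo, "10-DE maltodextrin (90% weight) and RT-175 caramel color (10% by weight) will be substituted for Novasoy" at equivalent weight, also two tablets a day. The paragraph adds that isoflavone content per tablet is held constant and that "we will use only one lot of Novasoy for the entire study".

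The Risk and Benefit Assessment gives a separate placebo figure, saying that maltodextrin "should have no biological effect at the dose, 150 mg, to be given to the subjects". It does not say whether 150 mg is per tablet or per day, or whether it is maltodextrin alone or maltodextrin plus colour.

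**The concern.** The dose defines the intervention and will be named in the trial's conclusion, so the product description should support it. Here the formula and the two-pill statement stand next to each other, are both expressed as aglycones, and disagree. No conversion between units closes the gap. The placebo weight given later does not match the described tablet either, which suggests that the two sections may have different tablets in mind.

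Two uses of the dose depend on the answer. Isoflavone intake is listed as an explanatory variable in Experimental Design and Methods, and Aim 3 models isoflavones together with other nutrients. If that variable is built from nominal pill content, the wrong content mis-scales it. The Risk and Benefit Assessment also rests part of its safety argument on earlier use at the dose planned here. The Introduction does not settle which figure is meant, because the earlier intakes of 100–200 mg cover both.

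**Working it through.** **Inputs.** From the Methods paragraph on the pills: 125 mg Novasoy, 50 mg isoflavones (aglycones), 60 mg sorbitol, 3 mg magnesium stearate, 412 mg dicalcium phosphate, 600 mg total; two tablets per day; placebo material 90% maltodextrin at equivalent weight. From the Abstract, Experimental Design and Methods, and the same Methods paragraph: 120 mg. From the Risk and Benefit Assessment: 150 mg placebo.

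**1. Does the described tablet add up?** 125 + 60 + 3 + 412 = 600 mg. It does, so 125 mg is not an isolated typing error.

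**2. Does it reproduce the stated dose?** Dose per dosing day = tablets × content = 2 × 50 = 100 mg. The stated 120 mg is not reproduced. The shortfall is 20 mg, or 1 − 100/120 = 16.7%. It would take 120/50 = 2.4 such tablets to reach 120 mg.

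**3. What would two tablets giving 120 mg require?** 120/2 = 60 mg per tablet. The described isoflavone fraction is 50/125 = 0.40.

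- Keeping 125 mg Novasoy: the fraction would have to be 60/125 = 48%, not 40%.
- Keeping 40%: Novasoy would have to be 60/0.40 = 150 mg. With the other weights unchanged the tablet weighs 150 + 60 + 3 + 412 = 625 mg. To stay at 600 mg by changing only dicalcium phosphate, that ingredient would be 600 − 150 − 60 − 3 = 387 mg, not 412 mg.

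None of these variants is in the document. They show only what the figures imply.

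**4. Does the described tablet give a 150 mg placebo dose?**

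| Basis | Per tablet | Two tablets |
|---|---|---|
| Placebo material | 125 mg | 250 mg |
| Maltodextrin (× 0.9) | 112.5 mg | 225 mg |

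None of the four values is 150 mg.

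**5. Can 150 mg be tied to 120 mg in another way?** Assume placebo material equals the Novasoy weight it replaces and the fraction stays at 40%.

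| Reading of 150 mg | Isoflavone equivalent of two active tablets |
|---|---|
| Material per tablet | 2 × 150 × 0.40 = 120 mg |
| Material per day | 150 × 0.40 = 60 mg |
| Maltodextrin per tablet | 2 × (150/0.9) × 0.40 = 133.3 mg |
| Maltodextrin per day | (150/0.9) × 0.40 = 66.7 mg |

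Under those assumptions only the first reading fits. A woman would then take 2 × 150 = 300 mg of placebo material (270 mg maltodextrin) per dosing day, and 150 mg would be a per-tablet weight, not the amount taken.

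**6. Effect on a nominal intake variable.** If 120 mg is entered and 100 mg was supplied: 120/100 = 1.20, an overstatement of 20%. If 100 mg is entered and 120 mg was supplied: 100/120 = 0.833, an understatement of 17%. Measured urinary and plasma isoflavones are unaffected.

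**The case against.** The formula is marked as an example, and the note after it turns to the volunteers in this study and gives 120 mg. Every stated daily dose is 120 mg; nowhere is a 100 mg daily dose stated. The example may have been carried over from another tablet. The 150 mg placebo remark, which is a safety comment and not a specification, can even be read as supporting a 60 mg tablet, leaving the example as the single outlier. The analytic harm is hypothetical, because the protocol does not say how isoflavone intake is calculated, and the primary mixed model compares randomised groups without using milligrams.

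Much of this stands. The document does not show that anyone received 100 mg, and the effect on the intake variable is conditional. It does not remove the defect. The example is the only product specification, and a tablet made to it would not deliver the dose stated next. If it is not the study tablet, the protocol does not specify the study tablet at all, although use of a single lot means that one definite formula should exist. Reading 150 mg as support for 120 mg requires an undescribed formula, the assumption that the 40% fraction carries over, and a per-tablet basis that the text does not state.

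**Conclusion.** The concern holds. Two tablets as described give 100 mg per dosing day against a stated 120 mg (50 against 60 mg per tablet). The 150 mg placebo figure has no stated basis and matches none of the four values that follow from the described tablet. These results rest only on the protocol's own figures. The inference that 150 mg belongs to a different, 60 mg tablet rests on the assumed 40% fraction and is not needed for the conclusion.

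The consequence is limited. The between-arm comparison, the power calculation and the measured isoflavone levels do not change. At stake are the dose named in the conclusion and, only if nominal content is used, an error of +20% or −17% in the pill part of the intake variable. This should be fixed, but it does not threaten the main result. Which figure is correct cannot be decided from the document.

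**What to change.** Reconcile the Abstract, Experimental Design and Methods, the Methods paragraph on the pills, and the Risk and Benefit Assessment against the manufacturer's record for the single lot supplied.

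- Give the study tablet's formula. Content per tablet × tablets per dosing day should equal one stated dose, and the ingredient weights should add to the tablet total.
- If the example formula is not the study tablet, say so and replace it.
- Make the placebo weight match the study tablet, and label it per tablet or per day, and as maltodextrin or total material.
- Use the reconciled figure in the conclusion. State how the isoflavone-intake variable is built and, if nominal pill content enters it, use the same figure there.

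The sponsor must say which figures are correct; no dose or schedule is proposed here. The cost is protocol wording and a check of one lot record, with no new data and no change to the between-arm analysis.

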MRI: MRI will be performed during the luteal phase of the menstrual cycle to control for small but detectable cyclical variations in breast density. MRI examination will be performed using GE Signa 1.5 Tesla MRI system. The study subject will be placed prone in the magnet with chest support to permit comfortable and unencumbered suspension of the breasts for imaging. In order to assure optimal MR signal uniformity, the breast will be imaged using the body coil. Coronal and axial multiple slices will be recorded to visualize the entire volume of the breasts. The proton density with and without fat suppression MRI images will be acquired for image analysis. The MR images will be networked to a version 4.0 GE Advantage Windows Workstation for processing and analysis of the breast tissues. A threshold algorithm will be applied to each image of the breasts to segment (separate) dense tissue. Using a 3-D image reconstruction algorithm, the multiple slices through the breast will result in a volume measurement of the entire breast and the dense tissue. In addition, a histogram function will be used to display the MR tissue signal distribution (mean and standard deviation) of the tissue type. Drs. [name] and [name] jointly will determine the appropriate threshold values to segment the dense tissues and the edge of the breasts. The volume of the entire breast, the dense tissue volume, and %-volume with dense breast are main outcomes of interest for statistical analysis.

Nipple fluid aspiration: Because several studies showed that isoflavones may be stimulatory to breast tissues, nipple fluid aspirates will be studied to help understand the mechanisms by which soy isoflavones may reduce breast density and have any affect on breast cell proliferation. A technique to aspirate breast nipple fluid from non-lactating women has been established in our laboratory. After compressing their breasts gently from all four quadrants, the

Fig. 9: Nipple fluid aspirator

subjects use a custom-made breast cup (basically a plastic funnel, Fig. 9) that is connected to a 10 ml-syringe. To apply suction, the plunger is pulled back to the 7-ml mark on the syringe and held at this pressure for 15 sec. If there is a keratin plug in the nipple, several initial suctions may be necessary to remove it. Once the keratin plug is removed, breast fluid can be recovered into a 200 μ l-capillary tube by applying negative pressures described above. The volume is measured (1 mm in capillary tube = 1 μ l). A portion of the nipple fluid is used for cytological evaluation for epithelial cells, and the remaining fluid transferred to phosphate buffer saline and stored at -80°C for later biochemical analysis. We will obtain fluids from secretors 4 times per year and make similar number of attempt to obtain fluid from non-secretors (8 times total during two year intervention). Repeated breast fluid samplings may increase fluid secretion. To understand the effect of samplings on breast fluid volume, nipple aspiration will also be repeatedly performed from non-secretors.

BMD (bone mineral density) measurement: The BMD (gm/cm^2) in the lumbar spine (L₂ to L₄) and hip will be measured using QDR® 4500A Fan Beam X-Ray Bone Densitometer (Dual Energy X-ray Absorptiometry, QDR® 4500A Fan Beam X-Ray Bone Densitometer, Waltham, Mass.). The densitometer is calibrated daily using a phantom. Daily spine phantom quality control scans will be preformed and adjusted to within 1% of the reference value. The coefficients of variation for the anatomic phantoms will be maintained <0.5%. This method was sensitive enough to detect BMD changes in pre- and post-menopausal women during tamoxifen treatment and in PEPI trial to measure BMD changes in women after only 1 year of 0.625 mg conjugated equine estrogen treatment. QDR® 4500 is a high performance fan-beam densitometry. T score and Z score will be calculated using NHANES reference data and with adjustment for weight and ethnicity. QDR® 4500A dual femur application measures both femurs in one quick scan and calculates the mean BMD of both femurs. The average gives better precision for monitoring changes.

Soy isoflavones have been shown to stimulate osteoblast cell activities in vitro. In ovariectomized animals, soy isoflavones increase bone mineral density. Because the soy isoflavones, daidzein and genistein, are not pure anti-estrogens. Our study population is premenopausal women who generally have high levels of endogenous estrogens. It is not clear what would be the net bone effects of soy isoflavones in premenopausal women. Moreover, soy isoflavones may have bone sparing effects independent of their estrogenicity. Therefore, it is important to know if the extent of displacement of ovarian hormone by soy isoflavones may affect bone density. Second, women with high BMD were also found to be at higher risk for breast cancer. Information on BMD will allow us to assess if BMD may be a useful surrogate biomarker for estimating breast cancer risk in future breast cancer prevention studies.

All scans will be performed in duplicate with the participants in the supine position. The duplicate scan is performed after participant gets off and then returns to the densitometer. Identical anatomical regions of interest, total hip, femoral neck, Ward triangle, the trochanter, and the intertrochanter areas, will be scanned during repeat scans

using a software feature of the DEXA program. The mean of the two scans will be used for statistical comparison with results at other times in the study.

Study Population: Subjects must be 30-40 years of age and be free of mammographic abnormalities. They must be willing and able to return to Galveston for scheduled study visits. We expect to enroll the 200 subjects required for the study within 6-8 months. Women will be excluded from the study if they are on contraceptive agents, any other exogenous hormones, or medications known to affect mammographic density; are pregnant or lactating; or have a previous history of cancer, breast augmentation or reduction, abnormal mammograms, or are at high risk for breast cancer (first degree relative with breast cancer). Women who are on any medically prescribed diet, or are not willing to be randomized will be excluded. Women with pacemakers or other permanent metal implants such as IUD will be excluded from the study. During initial screening, past history of allergic reactions to foods will be acquired. If subjects have prior histories of food allergies to soy food, they will be excluded. Subjects must have regular cycles and mid-luteal phase progesterone > 8 ng/ml. Perimenopausal women with > 100 pg/ml of serum estradiol on cycle day 2 and > 20 mU/ml FSH will be excluded. Enrollment will be available to all racial groups. Pregnancy will be excluded by measuring urinary hCG (human chorionic gonadotropins) by standard clinical testing procedure.

Recruitment: The following methods will be used to recruit study subjects. 1) We have purchased 20,000 name records from a marketing company (KM Lists, Marlton, NJ). This initial list purchased contained only 35 to 40 years old women living within 30-mile radius of Galveston. We plan to mail study advertisement brochure to every woman in this mailing list. If we cannot recruit sufficient subjects, we will purchase name records for women age younger than 35 and older than 30. The database includes age, race, address, date of birth, income, education etc. 2) Advertisement materials have been distributed thru email systems of UTMB, area women's organizations, health networks, local charities, churches, and beauty saloons. In this procedure, we usually contact a person who maintains an email mailing list and ask this person to email our advertisement information to those in the list. 3) Study information and recruitment are also posted on websites or bulletin boards after securing permission from appropriate authorities. 4) The advertisement brochure is also included in the reminder letter sent to area women by the UTMB Radiology Department for scheduling screening mammography. [PI note: We have not used this method since most of the women in this list are outside the age range of our inclusion criteria.] 5) Advertisement brochure will be left in the waiting area of mammography clinics, in local churches, beauty saloons and health fairs. 6) We will also advertise study in radio, TV and newspaper, if needed. [PI note: We have not advertised in newspaper, radio or TV because we found these methods not to be cost-effective in the past. We may not need to use these modes of advertisement since we are recruiting well with mass mailing. We do not do face-to-face recruitment of subjects in mammography waiting area of mammogram clinics.]

KM Lists is a direct marketing company. KM Lists is the list broker (a major wholesaler of Axiom's database) and Axiom is the list owner. The Axiom Infobase file is a compiled database made up from the white pages, voter registration, tax assessor

data, vehicle registration data, and many other sources. The Acxiom Corporation has a national database which includes approx. 116 million households. We purchased name records with age and gender restriction. According to KM Lists, the age information comes from household census, questionnaires, driver's licenses, credit bureau records, birth, high school and college records, warranty registrations, and insurance records. The gender information comes from Acxiom's proprietary conversion software. Both Acxiom and KM Lists rent the data out for many various direct mail/telemarketing campaigns and for research.

A similar telephone conversation is conducted for the potential subjects who telephone us and whom our staff telephones. The staff provides the purpose of the study, highlights the procedures involved, and describes the inclusion/exclusion criteria as detailed as the subjects wish to know. From this phone conversation, the subjects determine whether they want to come to UTMB for an inform consent visit. In general, most of the potential subjects call to find out if they are eligible and how they can be qualified for the study and to know more about the study procedures. No potential subjects would commit to come in for an inform consent visit unless they have sufficient information to assess that they will qualify for the study and know for sure that they like the study. If they are interested, they are then invited to come to the General Clinical Research Center of UTMB for a detailed description of the entire study as it stated in the consent form. During this visit, the content of the consent form is verbally presented to the study subject. After this presentation and answering their questions and concerns, the subject is encouraged to take time to read the consent form. If they are interested in the study, they sign the consent form. We then collect and record eligibility information. During this visit, the study schedule and remuneration chart included in the consent form is carefully described to subjects such that subjects understand our expectation of them and they understand what we will do for them. The subjects are given a signed copy of the consent form to take home and are encouraged to discuss the study with family member or friends. The subjects are informed in the consent form and during the consent visit that they can withdraw from the study anytime.

The subjects are given the Harvard DAQ, Personal Heath Questionnaire for Females (PHQF), and Menstrual Flow Chart and Supplement Intake Chart (MFC-DSC) to fill out. The PHQF is the standard of medical care forms to be filled out by patients visiting UTMB clinics including our GCRC, respectively. PHQF is the form used by UTMB Gynecology Clinic to collect reproductive history. The PHQF are reviewed by the physician investigators of this project as a part of history taking. Subjects can fill out these forms while at UTMB or they can take these forms home and fill out. For Spanish speaking only subjects, our Spanish speaking nurse from our GCRC or the Spanish speaking staff translate the questionnaires or forms and collect information by interview. The subjects also take urine jug, food records form home to fill out. The subjects are instructed on how to keep track of their cycle information. On the first day of their menstrual spotting (cycle day 1), they call our office to give us this date. From this date, we calculate when their luteal phase (post-ovulatory phase, the latter half of the menstrual cycle, usually cycle days 14 to 28) will be and days 20, 22 and 24 of their cycles. The

appointment is made for them to come in on these dates to have fasting blood draws and nipple fluid aspiration, to turn in their 12-hour urine collection and food records.

During this inform consent visit, the subjects are told that they may be removed from the study after certain diagnostic tests have been performed, for example, low progesterone level, abnormal mammograms, abnormal blood chemistries that cannot be resolved and if they are going through menopause.

The inform consent is performed by the authorized Study Coordinators or the PI. The PI visits and interacts with the study subjects frequently during their scheduled GCRC visits for clarifying study procedures, study purposes, and their concerns.

Post-intervention follow-up: The pills for both the placebo and isoflavone arms of the study contain multivitamins, including riboflavin and minerals. Riboflavin produces a bright yellow color in urine after intake. The study participants were blinded to treatment assignment per study protocol, but this would not prevent them from second guessing the study arm that they were assigned to. Our study participants probably would have noticed a change in their urine color whenever they ingested study pills, and this color change would indicate to the study team (we analyzed their urine) their degree of adherence to taking the study pills. Additionally, subjects might second guess the study arm that they were assigned to. The study subjects knew that they were taking multi-vitamins but were never told of a possible urine color change, and none of the subjects asked about this urine color change.

The purpose of this post-diet follow-up is to find out what these guesses were. We will email study participants who have received a dietary assignment. We would like each subject to choose one of these three answers in the email: (i) I believe that I took the placebo (sugar) pill, (ii) I believe that I took soy isoflavone pill, or (iii) I don't have an opinion about which of these I took. The frequency for each answer by treatment assignment and an interaction between treatment assignment and answer will be analyzed by ANOVA. We hypothesize that, due to the yellow coloring of their urine, a higher percentage of subjects would guess that they were in the active isoflavone treatment group, because most study participants prefer to be assigned to the active treatment group, if choice was allowed. This information will provide us with data about whether riboflavin can also be an effective masking agent for treatment group assignment in future clinical trials, not just as a tracer of compliance of taking study pills. Masking of treatment assignment would have an added benefit of balancing the participation behavior among study groups, in addition to randomization. We will send the questions initially by email and, if no response, by regular postal mail. We will request a dedicated email address from UTMB's Information Service for this specific purpose.

The survey questionnaire is not expected to change risk of participation.

Clinical Procedures:

The flow chart below outlines the study procedures and timeline in month (mo) for each subject:

Recruitment (mo 0) → Screening (mo 1) → Obtain baseline data (mo 2-3), give menstrual cycle calendar → Pregnancy test, followed by 1st mammography, DEXA bone density scan, and breast MRI → Randomization → Pill supplementation intervention (mo 4) → Outpatient visits to the GCRC twice in an assigned month and repeat this outpatient visit once every three months (4 times per year) to obtain treatment data (mo 4 to 15) → End of 1-year pill supplementation intervention (mo 15), review menstrual cycle calendar → Pregnancy test followed by 2nd mammography, DEXA bone density test, and breast MRI (mo 15) → Pill supplementation intervention continues (mo 15) → Outpatient visits to the GCRC twice in an assigned month and repeat this outpatient visit once every three months (4 times per year) to obtain treatment data (mo 15 to 26), review menstrual cycle calendar → End of 2-year pill supplementation intervention, end of study, pregnancy test, followed by 3rd mammography, DEXA bone density test, and breast MRI (mo 26)

1. Recruit volunteer subjects at UTMB Radiology Clinic or through TV, radio and newspaper advertisement and by mass mailing.
2. Invite potential subjects to UTMB GCRC for informed consent by the Study Coordinators or the PI. After obtaining written consent from the study subject, screening tests will be performed while as GCRC outpatient to determine eligibility.
3. Screening visits/Baseline visits: If the potential subjects reported that they have regular cycles and cycle lengths are in general longer than 24 days, they are unlikely to be peri-menopausal and their subsequent visits for these women are considered baseline visits. These visits will be scheduled during the luteal phase, i.e. 20 and 22 or 22 and 24 days after menstrual spotting depending on subject's cycle length. Cycle day 1 is the first day of menstrual spotting. The subjects are informed to call and report to us the date when they first detect menstrual spotting/bleeding as soon as possible and the staff will calculate when their cycle days 20, 22 and 24 will be and schedule their GCRC visits on these dates accordingly. The staff also checks with the subjects periodically to make sure that they do not forget to tell us the first day of their menstrual bleeding.

